### 9.1.1 Data Information Flow

The following personal data will be collected as part of the study: Name; Initials; Home Address; Sex at birth; Date of birth and Health Information. The Name; Home Address and Phone Number of the personal representative will be collected if required to obtain consent.

The name and address will only be collected for the purposes of sending a letter to the GP informing them their participant is taking part, to send the study questionnaires to the first 50 participants and to send consent forms (if required). This personal data will be kept at the study site.

Personal data will be stored by the study team on NHS computers (desktop and laptop). Computers will be password protected and kept in locked offices. All paper files containing personal data will be held in filing cabinets in NHS offices that will be locked when unattended. Access to the study documents will be by the study team only.

Personal data will also be stored on University computers hosting the study database. Edinburgh Clinical Trials Unit will provide and maintain a secure web based bespoke database compliant with the relevant regulations and Sponsor SOPs. Data will be entered by those staff delegated to do so on the delegation log held at site.

### 9.1.3 Data Controller

The University of Edinburgh and NHS Lothian are joint data controllers along with any other entities involved in delivering the study that may be a data controller in accordance with applicable laws (e.g. the site).

### 9.1.4 Data Breaches

Any data breaches will be reported to the University of Edinburgh and NHS Lothian Data Protection Officers who will onward report to the relevant authority according to the appropriate timelines if required.

## 10. STATISTICS AND DATA ANALYSIS

### 10.1 SAMPLE SIZE CALCULATION

A pragmatic sample size of 300 was based on projected recruitment over 12 months study period in around 15 centres. It is anticipated that this will provide sufficient data to demonstrate feasibility and inform design of a fully powered study

As a pilot feasibility study, no formal sample size calculation is appropriate. However, indicatively on the first primary outcome of recruitment feasibility, an acceptance rate of 50% would be estimated with a 95% confidence interval of 44% to 56% if 300 from 600 of those eligible agreed to be randomised. For the second primary outcome of death at 30 days, indicatively if the standard of care had a 30-day mortality of 35%,

with 300 randomised the study would have 90% power at a 5% level of significance to detect an approximate 50% relative reduction of 17%, to 18%.

## 10.2 PROPOSED ANALYSES

All statistical analyses will be governed by a comprehensive Statistical Analysis Plan authored by the study statistician and agreed by the independent Trial Steering Committee. As a feasibility pilot trial, all analyses will be exploratory and mainly descriptive. The primary outcome of recruitment feasibility will be assessed as the proportions who visited the ED that were (a) eligible, and then (b) of those who were eligible that were approached and then (c) of those eligible and approached the proportion that consented to be randomised. The clinical primary outcome of all causes mortality at 30 days will be summarised by randomised treatment group and then analysed using a mixed effects logistic regression adjusting for site and adjusting for pre-specified baseline covariates known to be strong predictors of 30-day mortality. The range of possible treatment effects indicated by the 95% confidence interval around the estimate of difference in 30-day mortality, and that around the 30-day mortality rate in the standard of care group will be used to inform the design of a definitive trial. We plan a number of important predefined exploratory sub-group analyses on the primary outcome including severity of illness at recruitment (NEWS/NEWS2, qSOFA, lactate), age, pre-existing known heart failure, pre-existent chronic kidney disease, baseline albumin. We will also undertake a subgroup analysis of primary outcome for all patients not admitted to a critical bed (HDU or ICU) If the data permits, we will consider additional analyses exploring compliance (what cumulative dose of novel intervention or standard care was received) using causal models with an instrumental variable approach. Secondary outcomes (e.g. volume of intravenous fluid, length of stay) will be analysed using mixed effects linear models, while the secondary outcomes involving proportions (e.g. proportion receiving renal replacement therapy, vasopressor infusion, invasive ventilation, readmissions within 90 days) will be analysed as per the primary outcome (with a mixed effects logistic regression). The proportions admitted to critical care (HDU or ICU) will be analysed using a proportional odds logistic regression. The safety outcomes will be analysed in a similar way according to their distribution. The quality of life data (at 180 days) will be analysed likewise with a model appropriate to the distribution. We will be interested in understanding the observed patterns of any missing data.

No formal cost-effectiveness analysis is planned, however, if data quality allows, an exploratory estimate of the incremental Quality Adjusted Life Years (QALYs) (at 180 days) and secondary care costs (at 30 days) will be made using the EQ-5D-5L. QALYs will be calculated by estimating a combined survival function and HRQoL function using the EQ-5D. Costs will be estimated by assigning national standard unit costs to inpatient stays (critical care and general ward level), readmissions and additional high costs activities observed in the study. Baseline (pre-admission) HQoL will be estimated using age/sex matched population reference data. In sensitivity analysis, surviving patients or proxies will be asked to provide a retrospective estimate of 1 month pre-admission modified EQ-5D-5L responses.

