### **3. STUDY DESIGN**

This trial will be an open label two-arm, multicentre, pragmatic, parallel group randomised trial of adult patients with community acquired sepsis recruited from the Emergency Department and Medical and Surgical Assessment Units across ~15 UK NHS Hospitals. The treatment phase will be the first 6 hours following randomisation. 30-day and 90-day follow up will be conducted using routine data only. The exception to this will be the first 50 patients enrolled in the study, Health Related Quality of Life (HRQoL) will be measured using the EQ-5D-5L at baseline, 7 days and at 180 days. At baseline, the participant or their relative will be asked to recall the quality of life 4 weeks prior to the index hospital admission (modified EQ-5D-5L). Questionnaires will be administered by direct participant/relative completion or postal survey with telephone follow up for non-responders after two mailings two weeks apart.

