# As Day 30 and Day 90 follow up is collected from the medical records it can be reviewed and recorded in the eCRF up to 7 days after the time point so it captures all admissions/events up to and including Day 30 and 90.

For the first 50 participants enrolled in the study, HRQoL will be measured using the EQ-5D-5L at baseline, 7 days and at 180 days. If questionnaires are not completed on the specified day or are not returned by the participant, this will not be reported as a deviation. Vital status will be checked either using local electronic medical records or contact with participant GP prior to contacting participant. Outcome measures will be obtained via the medical notes.

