#### 4.8 Other analyses

For the health economics analyses, EQ-5D-5L index score will be calculated from individual health profiles using UK preference weights. Mean, standard deviation (SD), minimum, median, and maximum scores will be provided for the study population by visit and by randomised treatment. The EQ VAS score (between 0 and 100) will be summarised using mean, SD, minimum, median and maximum scores by visit and by randomised treatment. Patients who are dead at the time of sampling will be assigned a zero index score and a missing VAS response. The numbers and rates of missing data will be reported per measure for each visit.

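### No 180-day EQ-5D-5L or QALY comparison is specified to adjust for the baseline EQ-5D-5L planned in the first 50 participants (low priority)

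*Protocol*

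**What the plan says.** - **Collection.** Protocol section 3 states: "Health Related Quality of Life (HRQoL) will be measured using the EQ-5D-5L at baseline, 7 days and at 180 days". This applies to the first 50 enrolled. The baseline form is a recall: "At baseline, the participant or their relative will be asked to recall the quality of life 4 weeks prior to the index hospital admission". The schedule in section 7.1 places it on Day 0. Section 7.1 also tolerates gaps: "If questionnaires are not completed on the specified day or are not returned by the participant, this will not be reported as a deviation".
- **QALY estimate.** Protocol section 10.2: "Baseline (pre-admission) HQoL will be estimated using age/sex matched population reference data". The next sentence reads: "In sensitivity analysis, surviving patients or proxies will be asked to provide a retrospective estimate of 1 month pre-admission modified EQ-5D-5L responses". The analysis is exploratory: "No formal cost-effectiveness analysis is planned, however, if data quality allows, an exploratory estimate of the incremental Quality Adjusted Life Years".
- **180-day quality of life.** Protocol section 10.2: "The quality of life data (at 180 days) will be analysed likewise with a model appropriate to the distribution". No baseline term is named.
- **SAP.** Section 4.8 says that EQ-5D-5L index "scores will be provided for the study population by visit and by randomised treatment", and that participants who have died score zero on the index. Section 4.6(b) models other continuous outcomes with site as a random effect and names no baseline value of the outcome. Section 3 places health economic analysis outside the SAP, so protocol section 10.2 is the only QALY specification supplied.

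**The concern.** Population norms are identical for any two people of the same age and sex. They cannot reflect a chance difference between arms in comorbidity or frailty. An individual pre-admission value is planned for the same 50 people and could do so, but no analysis is specified to use it as a covariate. In a subset this small, imbalance in prior health can shift the 180-day difference noticeably, and the interval is wider than it need be. Protocol section 1.1 says that the definitive study will include a health economic evaluation, so the pilot is a natural place to settle how baseline is handled.

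**Working it through.** **Inputs from the documents.** 50 participants and 1:1 allocation (protocol sections 3 and 5.5.1) give about 25 per arm. Deaths score 0 (SAP section 4.8). Forms fall at days 0, 7 and 180. The documents give no EQ-5D figure to reproduce.

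**Assumed, because the documents are silent.** SD of the index 0.25 to 0.35; correlation between baseline and 180-day index in survivors 0.4 to 0.7; mortality 20% to 35%; 16 to 25 analysable per arm.

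**1. Chance imbalance.** The standardised baseline difference has SE √(2/n).
- n = 25: SE = 0.283. P(|difference| > 0.3 SD) = 29%; P(> 0.5 SD) = 8%.
- n = 16: SE = 0.354. The same probabilities are 40% and 16%.

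On the utility scale with SD 0.3, one SE is 0.3 × √(2/25) = 0.085. Take a survivor slope of 0.5. With deaths at zero and unrelated to baseline, the slope becomes 0.5 × 0.80 = 0.40 at 20% mortality and 0.5 × 0.65 = 0.325 at 35%. A one-SE imbalance then moves the 180-day difference by 0.085 × 0.40 = 0.034 or 0.085 × 0.325 = 0.028.

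**2. Unadjusted precision.** The 95% half-width is 1.96 × SD × √(2/25): 0.139, 0.166 and 0.194 for SD 0.25, 0.30 and 0.35.

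**3. Gain from adjustment.** With one covariate and N = 50, the variance ratio is (1 − r²) × (1 + 1/(N − 4)) = (1 − r²) × (1 + 1/46). Here r is the correlation in the analysed outcome, zeros included, and the zeros dilute it. Simulating death independent of baseline (survivor mean 0.6, SD 0.25):

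| Survivor correlation | Mortality | r with zeros | Variance cut |
|---|---|---|---|
| 0.5 | 20% | 0.305 | 7% |
| 0.5 | 35% | 0.230 | 3% |
| 0.7 | 20% | 0.425 | 16% |
| 0.7 | 35% | 0.323 | 8% |

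A survivor correlation of 0.4 with 35% mortality gives r of about 0.21 (survivor SD 0.3) and a cut of about 2%. The range is therefore roughly 2% to 16%, which narrows the interval by about 1% (√0.98 = 0.99) to 8% (√0.84 = 0.92).

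If the odds of death instead rise 1.5- to 2-fold per SD of worse baseline, with survivor correlation 0.5 to 0.7, the simulated cut is about 13% to 32%. At 30% the interval narrows by about 16% (√0.70 = 0.84).

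**4. Norms or recall as the QALY starting value.** In a day 0/7/180 trapezoid, the day-0 value carries 3.5/180 = 1.9% of the area. Swapping norms for recall at day 0 barely moves the QALY. With days 0 and 180 alone it would carry 50%, but a day-7 form is planned. The benefit comes from the covariate, because prior health also acts through the later values.

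**The case against.** The strongest case against is that nothing here is biased. Randomisation protects the unadjusted difference, the analysis is exploratory and conditional on data quality, and with a half-width near 0.17 no conclusion turns on it. That stands, and it sets the priority.

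Four stronger readings are tempting, and the documents do not support them:
- *The recalled data are wasted.* They are demoted. They feed a sensitivity analysis, and the SAP reports the baseline visit by arm.
- *No comparison will adjust for baseline.* None is specified to. The protocol leaves the 180-day model open, and health economics lies outside the SAP.
- *The sensitivity analysis conditions on survival.* Section 10.2 admits proxies, who can answer for a participant who has died. The wording is loose and differs from section 3, but survivor selection is not established.
- *Adjustment would remove the full squared survivor correlation, such as 25% of variance at 0.5.* That ignores the zero score for deaths.

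A further objection concerns the covariate itself. The trial is open label, and consent may be deferred (section 5.2.3) or sought from the participant on recovered capacity (section 5.2.4), so a recall form could be completed with the arm or clinical course known. Adjusting for such a value could introduce bias. This is a fair restriction on which values to use, not a reason to leave baseline out. Recall error in acute illness is also a plausible reason to prefer norms in the base case, although the documents do not give it.

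**Conclusion.** The point holds as a minor omission. A baseline EQ-5D-5L is planned for the first 50, and no 180-day index or QALY comparison is specified to adjust for it. The cost is chance imbalance left in place and some lost precision, without bias. The imbalance probabilities rest only on n per arm and a normal approximation. The variance figures rest on an assumed correlation, mortality and link between baseline health and death. The upper end is not far-fetched: protocol section 1.1 says that mortality is higher in older patients, and SAP section 4.4 treats cancer and heart failure as strong predictors of 30-day death. Replacing norms by recall as the QALY starting value is a matter of preference, and this point does not depend on it. Full collection in all 50 is planned but not assured.

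**What to change.** 1. In protocol section 10.2, and in SAP section 4.8 or the health economics plan, estimate the 180-day index and QALY differences by regression on arm, measured baseline EQ-5D-5L index and a self/proxy indicator.
2. State a simple rule for missing baseline that ignores arm and outcome, for example filling with the age/sex norm.
3. Keep the norm-based QALY estimate and report it alongside.
4. Reconcile section 3 (asked at baseline, participant or relative) with section 10.2 (survivors or proxies asked retrospectively): say who is asked and when.
5. Use as covariate only values recorded before allocation or before the outcome is known, and treat other values as missing under rule 2.

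Cost: a wording change and two model terms, with no new questionnaire. Recall and proxy error weaken the adjustment. The second term raises the small-sample factor from 1 + 1/46 to 1 + 2/45, about two percentage points, so at the weakest correlations the net precision gain is close to nil.

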## 11. PHARMACOVIGILANCE

The Investigator is responsible for the detection and documentation of events meeting the criteria and definitions detailed below.

5% Human Albumin Solution has a well-documented safety profile. Although the Summary of Product Characteristics suggests that rare cases of anaphylactic events might be associated with albumin administration, there is no evidence that the albumin treatment regime used in this trial is associated with an increased risk of anaphylaxis. Nevertheless, data on anaphylaxis events will be collected as secondary outcomes and will be presented to the independent Data Monitoring Committee (DMC) for unblinded review.

Full details of contraindications and side effects that have been reported following administration of the IMP can be found in the relevant Summary of Product Characteristics (SPC) Booklet.

### 11.1 DEFINITIONS

An **adverse event** (AE) is any untoward medical occurrence in a clinical trial participant which does not necessarily have a causal relationship with an investigational medicinal product (IMP).

An **adverse reaction** (AR) is any untoward and unintended response to an IMP which is related to any dose administered to that participant.

A **serious adverse event** (SAE), **serious adverse reaction** (SAR). Any AE or AR that at any dose:

- results in death of the clinical trial participant;
- is life threatening\*;
- requires in-patient hospitalisation^ or prolongation of existing hospitalisation;
- results in persistent or significant disability or incapacity;
- consists of a congenital anomaly or birth defect;
- results in any other significant medical event not meeting the criteria above.

\*Life-threatening in the definition of an SAE or SAR refers to an event where the participant was at risk of death at the time of the event. It does not refer to an event which hypothetically might have caused death if it were more severe.

^Any hospitalisation that was planned prior to enrolment will not meet SAE criteria. Any hospitalisation that is planned post enrolment will meet the SAE criteria.

A **suspected unexpected serious adverse reaction** (SUSAR) is any AR that is classified as serious and is suspected to be related to the IMP, that it is not consistent with the information about the IMP in the Summary of Product Characteristics (SPC) booklet or Investigators Brochure.

### 11.2 IDENTIFYING AEs AND SAEs

Participants will be asked about the occurrence of AEs/SAEs during the study and the medical records will be reviewed to identify these. AEs and SAEs will only be recorded and reported from consent until 7 days after randomisation due to the well-known safety profiles of the interventions. Open-ended and non-leading verbal questioning of

the participant will be used to enquire about AE/SAE occurrence. Participants will also be asked if they have been admitted to hospital, had any accidents, used any new medicines or changed concomitant medication regimens. If there is any doubt as to whether a clinical observation is an AE, the event will be recorded.

AEs and SAEs may also be identified via information from support departments e.g. laboratories.

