### **5.2.3. Deferred Consent**

Patients who have “life threatening features” and who lack temporary capacity due to their current illness can be recruited to the trial using deferred consent if there is no Personal/Professional Representative to give consent on their behalf within 30 minutes so that treatment can be commenced within one hour. The decision to defer consent should be made by an ST4 (or above) or consultant who has appropriate trial training and this should be clearly documented.

The patient would be enrolled into the trial and receive their allocated treatment. Consent would be sought as soon as possible from a Personal Representative (or a Professional Representative if they are available sooner). If a Personal/Professional Representative declines to give consent for continuation at this stage, their wishes will be respected and the withdrawal process in section 5.6 will be followed.

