## 8. DATA COLLECTION

Data will be collected from consent until final follow up visit. Site-specific source data plans will be created to indicate where protocol required information will be originally documented. Source data worksheets created by the Edinburgh Clinical Trials Unit (ECTU) will be made available, but their use is optional. The eCRF can be used as source data for some data points (this should be noted on the source data plan by the site).

Study data will be entered onto an eCRF (case report form) developed by ECTU.

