### 11.5 RECORDING OF AEs

All adverse events identified between consent and 7 days after randomisation for each participant will be recorded in the medical notes for each participant. Only those events which would meet the criteria of seriousness and also qualify for reporting to the sponsor (see section 11.6.2) will be recorded on AE logs/ SAE forms and will be assigned the appropriate MedDRA Systems Organ Class (SOC) code.

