### **11.6.2 Reporting of SAEs/SARs/SUSARs and exemptions**

All SAEs that meet the definition given in section 11.1 and occur between consent and 7 days afterwards should be reported to the Sponsor unless they meet the exemption criteria below. These are outcome events are anticipated to occur in this participant group and will be exempt from reporting to the Sponsor:

Death related to infection (including multi-organ failure)

Critical care (HDU/ICU) admission

Acute kidney injury

Pulmonary oedema,

Allergy or anaphylaxis

Events That Are Common in the Trial Population:

The primary event of infection is classified as a pre-existing condition. As such, the occurrence or expected progression of infection or sepsis-related events including death will occur. In addition, participants are likely to have many minor adverse events during the course of the trial. These events will be recorded in the medical records and assessed in the same way as AE/SAEs. However, they are not usually recorded as AEs/SAEs, unless they are thought to be related to participant involvement in the trial.

Abdominal pain, nonspecific or related to a pre-existing condition

Accidents (domestic, traffic, occupational) including falls

Agitation or Anxiety

Atrial fibrillation or another cardiac dysrhythmia

Bleeding

Blood result abnormality (outside lab reported normal range) requiring no clinical intervention

Breathlessness related to a pre-existing condition e.g. COPD

Chest pain, non-specific or related to a pre-existing condition

Confusion or delirium

Constipation

Deep vein thrombosis/venous thromboembolism

Diarrhoea and/or vomiting

Dizziness or light headedness including vertigo

Dysphagia

Embolism

Fatigue, tiredness or sleepiness (somnolence)

Gastrointestinal disturbance, non-specific

Headache

Hypotension (if related to infection)

Hypoxia (if related to infection)

Incontinence, urinary or faecal

Malignancy, new diagnosis or new treatment for existing diagnosis

Mild ankle swelling not requiring treatment

Mood disorders

Muscle twitching

Any musculoskeletal condition e.g. arthritis or mechanical back pain

Peripheral vascular disease

Pneumothorax

Pressure sores or skin ulceration

Procedures occurring as part of the management of infection e.g. urinary catheter, central venous line, arterial line, intubation

Seizure

Sinus tachycardia (if related to infection)

Visual Loss e.g. cataract or macular degeneration or retinal detachment

Weight loss

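### The AE/SAE window opens at consent, so for deferred-consent participants serious events and suspected reactions between randomisation and later consent can fall outside AE/SAE logging and sponsor reporting

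*Protocol*

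**What the plan says.** **Start of the window.** Protocol 11.2: "AEs and SAEs will only be recorded and reported from consent until 7 days after randomisation". Protocol 11.6.2 asks for SAEs that "occur between consent and 7 days afterwards should be reported to the Sponsor unless they meet the exemption criteria below". Protocol 11.5 is looser: "All adverse events identified between consent and 7 days after randomisation" go into the medical notes, and only the serious, sponsor-reportable ones go onto AE logs and SAE forms.

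**Treatment before consent.** Protocol 5.2.3 covers patients with life-threatening features who temporarily lack capacity and for whom no representative can be found within 30 minutes. For them, "The patient would be enrolled into the trial and receive their allocated treatment"; a representative's consent is requested afterwards, as soon as possible and with no time limit. Protocol section 3: "The treatment phase will be the first 6 hours following randomisation".

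**Related rules.** Protocol 11.3.1 treats a condition that existed before informed consent as medical history unless it is judged to have worsened. Protocol section 8: "Data will be collected from consent until final follow up visit". SAP 4.7 tabulates adverse events by treatment group and states no window of its own, so it takes whatever the protocol rule lets through.

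**The concern.** For most participants consent comes before randomisation, and a window that opens at consent covers all exposure to study fluid. For the deferred route the order is reversed: randomisation, fluid, then consent. Part or all of the exposure can then precede the opening of the window.

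Acute reactions to a resuscitation fluid are most likely while it is being given, and 5.2.3 reserves this route for patients with life-threatening features. A gap here means that safety follow-up differs by consent route and is weakest in a severely ill group at the time of exposure. The events affected are those with no other route into the trial data: serious events that are neither on the 11.6.2 exemption list nor a named outcome, including an unexpected serious reaction of the kind that 11.7 is meant to send to the regulator.

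**Working it through.** The plan states no figure to reproduce. The check is a comparison of texts, followed by simple arithmetic on assumed delays.

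**1. When the window opens**

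| Section | Start | End | Keyed to |
|---|---|---|---|
| Protocol 11.2 | consent | 7 days after randomisation | recording and reporting |
| Protocol 11.5 | consent | 7 days after randomisation | identification |
| Protocol 11.6.2 | consent | 7 days after consent | occurrence |

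Section 11.6.2 excludes pre-consent events most plainly. Section 11.2 does so on its natural reading, because of its restrictive wording. Section 11.5 could admit an earlier event that is found in the notes after consent.

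**2. Order of events by consent route**

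- Patient or representative consent in advance: consent, randomisation, fluid. Uncovered exposure is 0 h.
- Deferred consent (5.2.3): randomisation, fluid, consent. Uncovered exposure runs from randomisation to consent, or to the end of treatment if that is sooner.

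No section sets another start for the second route. Nor is it said which consent opens the window: 5.2.3 and 5.2.4 allow for a personal representative, a professional representative and the recovered participant, and these can come at different times.

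**3. What is lost and what is not**

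- Acute kidney injury, pulmonary oedema and allergy or anaphylaxis form secondary endpoint 11 (2.2.2). The schedule in 7.1 marks them at discharge, SAP 4.6 item 7 summarises them, and their definition has no consent-based start. Mortality and critical care admission are also outcomes in their own right.
- Section 11.6.2 exempts those named complications, infection-related death and critical care admission from sponsor reporting for everyone. Under 11.5 only sponsor-reportable serious events reach the AE log. The exempt events would therefore be off the log whatever the consent route.
- What remains, and can be lost, is the non-exempt SAE or suspected reaction. It has no named-outcome route.
- Section 11.3.1 adds to this: a condition first arising after study fluid but before deferred consent existed before informed consent, and so may be classed as medical history.

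**4. Share of the treatment phase left uncovered**

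Uncovered share = min(gap, 6) / 6, where gap is the time in hours from randomisation to consent and 6 h is the treatment phase in Protocol section 3. The gaps are assumptions, because the documents give none.

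| Gap | Calculation | Uncovered |
|---|---|---|
| 1 h | 1/6 | 17% |
| 2 h | 2/6 | 33% |
| 4 h | 4/6 | 67% |
| 6 h or more | 6/6 | 100% |

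**5. Number of participants**

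Affected = 300 × deferred share. The share is also an assumption: 2%, 5%, 10%, 20% or 30% would be 6, 15, 30, 60 or 90 participants.

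**6. Close of the window**

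Measured from randomisation, 11.2 and 11.5 close at 7 × 24 = 168 h, and 11.6.2 closes at 168 h plus the gap. The two ends differ by exactly the consent delay: almost nothing with consent in advance, but a full day if, for example, consent comes at 24 h.

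**The case against.** The strongest reply is that other text points towards capture.

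- The schedule in 7.1 marks adverse events at Baseline (Day 0), the same column as randomisation and fluid administration. That is true, but a mark in a day column sets no starting time and does not displace the restriction in 11.2.
- Section 11.6 requires an SAE in a study participant to be reported within 24 hours of awareness, without mentioning consent. But 11.6.2 then defines which SAEs are reportable, and does so by occurrence after consent.
- Section 9 says that all adverse event data will be collected and reported as the authorities require. That sentence belongs to the rule for withdrawn or refused consent and for death without participant consent; it sets no general window.
- Section 11.2 says to record in case of doubt. The doubt meant there is whether an observation is an adverse event, not whether it falls within the window.
- Section 5.5.1 has all outcomes recorded once a patient is randomised. This supports the named outcomes but does not set the AE/SAE window.
- Sections 5.2.4 and 9 order destruction of data already collected when consent is never obtained. The protocol therefore clearly expects some collection before consent, which makes the section 8 wording a matter of alignment rather than a serious fault.

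Two parts of the reply stand. Section 11.5 keys on identification and can be read to admit earlier events. And a reader might infer that all acute harms in deferred-consent participants escape the trial, or that the whole treatment phase is always lost. The documents support neither: the main anticipated fluid complications are separate outcomes, anaphylaxis data go to the Data Monitoring Committee under section 11, and the full 6 hours is lost only if consent takes 6 hours or more, while 5.2.3 asks for it as soon as possible.

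**Conclusion.** The point holds in a limited form. Sections 11.2 and 11.6.2, and less clearly 11.5, open AE/SAE recording and sponsor reporting at consent; 5.2.3 puts allocated treatment before consent; and nothing reconciles them. Read literally, non-exempt SAEs and suspected reactions in that interval are outside the AE/SAE log, sponsor and SUSAR reporting, and the SAP 4.7 tables, and 11.3.1 could relabel them as history. The conflict over the closing date is plain on the face of the text.

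The size cannot be fixed from the documents. It depends on two unstated quantities, the share recruited by deferred consent and the delay to consent, and the ranges above are illustrations only. The route is narrow and the delay may be short. Even so, this is a stated rule that can exclude serious reactions during exposure, which is more than a missing detail, and it should be corrected.

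**What to change.** - **11.2, 11.5 and 11.6.2:** use one window for every consent route: events *occurring* from randomisation (or from consent, if earlier) until 7 days after randomisation. This also removes the two closing dates and the difference between identified and occurring.
- **11.3.1:** define pre-existing as present before randomisation (or before consent, if earlier). Without this, events newly brought into the window could still be filed as medical history.
- **Section 8:** start data collection at the same point.

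With this wording the uncovered part of the treatment phase is 0 h for every route, and SAP 4.7 takes on the corrected window. The rules in 5.2.4 and section 9 on destroying data when consent is never obtained stay as they are; any safety information lost through them is a separate matter that this change does not repair.

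The cost is wording in five protocol sections and a few more events to enter for deferred-consent participants, from medical records that 11.2 already has sites review.
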